## 6 Risks and Safety Assessment

Ketone Ester: This proposal includes a ketone ester which is commercially available and has been granted "Generally Regarded as Safe" (GRAS) status from the FDA. This KE undergoes complete enzymatic hydrolysis to form BHB (and R-1,3-butanediol) by carboxylesterases expressed widely, including the gastrointestinal tract, liver and blood. R-1,3-butanediol, itself, is further metabolized in the liver and blood to produce BHB. The TMax ranges from ~1-3 hours. Elimination is accomplished via conversion to acetone and lung exhalation, renal elimination, and uptake by tissues using for conversion to ATP (including the brain, heart, kidney, and skeletal muscles). We exclude participants both with a history of significant renal impairment (eGFR <25 ml/min/m^2) or hepatic impairment (history of cirrhosis, alcohol abuse). Peak concentrations of KE are reached around 60 minutes at doses anticipated to be administered here. The half-life of BHB from the compound is 0.8-3.1 hours. Adverse effects are infrequent and dose-dependent; gastrointestinal distress occurs at the highest levels of administration (714 mg/kg), consistent with our own experience. No clinically significant changes in vital signs, lipid levels, blood counts, renal function, and urinalysis parameters were observed at doses similar to those studied here. Participants may be on SGLT2i which are minimally ketogenic medications in themselves with minimal risk for ketoacidosis in HF. As outlined in this section, it is not anticipated that the KE will amplify risk of ketoacidosis with SGLT2i given the differing biologies of endogenous versus exogenous ketosis. However, this potential risk will be outlined to participants who enroll in this study. **Dose:** In this proposal, we will perform a pharmacokinetic study to determine optimal dose without significant safety concerns which will be explored in our pharmacokinetic study. Our product is purchased commercially as "DeltaG" (TdeltaS, Orlando, FL). We have administered these doses proposed here to 15 HFpEF patients in an ongoing study without significant adverse events related to the nutraceutical. We will monitor for any adverse events throughout the study visit. The compound half-life is short as indicated above. To aid intolerability, participants are served a light meal. In addition, water (which may be naturally flavored and/or carbonated) is freely permitted.

**Phlebotomy and blood draws:** We leverage healthcare professionals who have experience in blood draws and maintaining venous catheters in our study. Risks from the peripheral (e.g. antecubital fossa) venous catheterization include minor discomfort, minor bruising, bleeding, hematoma and/or fainting associated with the drawing of blood. There is also a very small chance (less than 1%) of infection at the blood draw site. The amount of blood to be drawn during each study is modest (100 mL).

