We now have a unique opportunity to study a ketone ester (KE), (R)-3-hydroxybutyl (R)-3-hydroxybutyrate (commercially known as "DeltaG"), that provides systemic ketosis in a deep phenotyping study of HF patients. Initial studies of DeltaG demonstrated significant improvement in exercise capacity among endurance athletes. In this first study, we attempt to find the optimal dose of the ketone product. As patients may be taking minimally ketogenic medications (SGLT2 inhibitors), we will study the pharmacokinetic effects of ketone ester with patients on, and not on, these medications.

Our Specific Aims are as follows:

Aim 1. To assess the pharmacokinetics and safety of ketone ester in patients on, and not on, SGLT2 inhibitors. We will perform serial peripheral blood sampling to understand the effects of acute ketone ester on pH, glucose, systolic blood pressure, and ketone levels to find an optimal dose of the product.

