#### 4 Published Data on Ketone Ester

DeltaG is a ketone ester (KE) that undergoes complete enzymatic hydrolysis to form BHB (and R-1,3butanediol) by carboxylesterases expressed widely, including within the gastrointestinal tract, liver, and blood. R-1,3-butanediol, itself, is further metabolized in the liver by first-pass metabolism and blood to produce BHB by alcohol dehydrogenase and aldehydye dehydrogenase. BHB undergoes further metabolism to acetoacetate and acetone, though only BHB and acetoacetate are taken up by extra hepatic tissues as energy sources.

KE is eliminated through at least first order kinetics and capacity limited elimination. Elimination is accomplished via 3 predominant means, including (1) conversion to acetone and lung exhalation, (2) renal elimination (of BHB and acetoacetate, though this contribution is negligible particularly during exercise), and (3) uptake by tissues using monocarboxylate transporters for conversion to ATP.

Concentrations of the KE compound of roughly 3-5 mmol/L are reached within 60 minutes at doses comparable to what is studied here. The half-life of the compound is 0.8-3.1 hours. The KE compound has a very favorable safety profile with adverse effects limited to dose-dependent, gastrointestinal distress that typically occur only at the highest levels of administration (714 mg/kg).

Request for IND exemption: We believe this study qualifies under the criteria for IND exemption. DeltaG has been granted **GRAS** status through the FDA as a food, and the GRAS documentation will be separately submitted. We believe this study is exempt from the IND requirements because it meets the conditions of FDA guidance (sections VI.D.1 & VI.D.2). Specifically, DeltaG, as used in this study, is not intended for use "in the diagnosis, cure, mitigation, treatment, or prevention of disease". As DeltaG is only received on *one* study date as an acute study, and endpoints assessed here are for safety, we believe the use of DeltaG fulfills these critiera here. Participants will be notified in the ICF specifically that they will not benefit as a result of participating in the study. The intent of the study is to describe the acute effect of DeltaG (a food) on venous pH, glucose, and blood pressure as a safety mechanism. In addition, the results of this study are not intended to affect the marketing or labeling of DeltaG.

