## 5.3 Pharmacokinetic study:

SGLT2i are standard-of-care ketogenic medications in HFrEF that minimally raise ketone levels though still well within normal limits (0.10mM to 0.13mM, normal <~0.5mM) through reducing insulin:glucagon ratio. Since exogenous ketones *increase* this ratio as shown in our previous work and *reduce* endogenous ketosis, the combination of exogenous ketones and SGLT2i is not expected to perpetuate ketoacidosis risk by SGLT2i (which has not been a significant concern in clinical trials of HFrEF). Further, recent work has supported the safety of ketogenic interventions in patients taking SGLT2 inhibitors. Additionally, pH changes with robust ketosis by KE are noted (1 study showed a pH decrease of 0.10 to an arterial pH of 7.31 after the ketone drink as an expected change). Nevertheless, we will first perform a dose-finding study in 10 HFrEF participants on SGLT2i and 10 not on SGLT2i to assess safety (Table 1). We will measure venous pH, glucose, blood pressure, and BHB every 60 minutes for 4 hours. After a standardized meal containing carbohydrate (to limit endogenous ketosis), we will assess 5 participants in each stratum using 250 mg/kg to initially target BHB levels ~1-2 mmol/L, and then dose escalate to 500 mg/kg for 5 participants which is predicted to achieve BHB levels ~3 mmol/L (safely achieved in HF patients previously with KE without inducing significant side effects including mild acidosis). This is also the dose used in a recent trial in cardiogenic shock without significant safety concerns but with significant efficacy. We will not escalate past 500 mg/kg given increasing risk for gastrointestinal symptoms.9, 37

Table 1. Pharmacokinetic Stud	y Details and Dose Escalation/De-escalation Plan

Strata	Dose	Timepoints assessed	Endpoints assessed
SGLT2i arm and no SGLT2i arm	250 mg/kg KE for 5 participants, then 500 mg/kg for 5 participants	Every 60 minutes for 4 hours	Venous pH, systolic blood pressure, glucose

Food may be provided to participants if they have hypoglycemia (glucose <55 mg/dl) but otherwise we will ask participants to refrain from consuming food after the ketone drink is administered until the 4 hour blood draw.

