## 7 Statistical analysis plan

Primary outcomes

- 1. Venous pH at 1 hour
- 2. Systolic blood pressure at 1 hour
- 3. Glucose at 1 hour
- 4. Beta-hydroxybutyrate level at 1 hour

Participant characteristics will first be summarized using means (standard deviations), medians (interquartile range), and counts (percentages) as appropriate for the type of variable and its distribution. We will plot summary estimates of venous pH, glucose, ketone levels, and systolic blood pressure over time, overall and stratified by SGLT2i use and ketone ester dose. We will compare whether achieved venous pH, glucose, ketone levels, and systolic blood pressure vary by background SGLT2i use, accounting for related baseline measurements. Sensitivity analysis will adjust for age, sex, ketone ester dose, eGFR, and hemoglobin a1c (if available). Repeated measures techniques (accounting for clustering at the level of the participants) may be used to assess overall changes in pH, ketone levels, systolic blood pressure, and glucose. We will describe peak ketone concentrations achieved by arm. Similarly, we will assess the relationship between peak ketone levels (dependent variable) and dose of KE (independent variable). P<0.05 will be used to indicate statistical significance.

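### Gastrointestinal distress is the stated reason for the 500 mg/kg ceiling, but no tolerability measure informs the choice of dose and section 7 summarises no adverse events by dose

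*Combined protocol and SAP*

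**What the plan says.** Three places in the combined protocol and SAP identify gastrointestinal effects as the tolerability issue.

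- Section 4 describes "adverse effects limited to dose-dependent, gastrointestinal distress that typically occur only at the highest levels of administration (714 mg/kg").
- Section 6 says much the same: "Adverse effects are infrequent and dose-dependent; gastrointestinal distress occurs at the highest levels of administration (714 mg/kg").
- Section 5.3 uses it to set the ceiling: "We will not escalate past 500 mg/kg given increasing risk for gastrointestinal symptoms".

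The measures for choosing a dose are stated separately. Aim 1 in section 2 covers pharmacokinetics and safety, and will examine "the effects of acute ketone ester on pH, glucose, systolic blood pressure, and ketone levels to find an optimal dose of the product". Table 1 in section 5.3 lists pH, systolic pressure and glucose as endpoints. Section 7 names four primary outcomes, which are those three plus BHB, each at 1 hour. Section 7 breaks down only these four measures by dose, and the only relationship with dose that it examines is that of peak ketone level.

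Section 6 describes the purpose as to "determine optimal dose without significant safety concerns which will be explored in our pharmacokinetic study". On symptoms it says "We will monitor for any adverse events throughout the study visit". The documents give no symptom instrument, assessment times, grading or summary, and they do not say whether the amount of drink taken is recorded.

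**The concern.** Section 1 says the result will inform dosing in a later randomized trial. A dose recommendation from this study should therefore be able to say something about tolerability at each dose. As written, the one adverse effect that the documents call dose-dependent has no outcome status, no defined collection and no place in the analysis.

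General monitoring protects the participant during the visit, but it does not by itself yield counts that can be set side by side. The 250 mg/kg cohort is dosed first and the 500 mg/kg cohort afterwards, and no blinding is described. Without a fixed set of questions, what is asked and noted could differ between cohorts. Mild symptoms that nobody asked about at the visit cannot be recovered later. The same applies to the share of the drink taken, which a reader needs in order to interpret the relationship between peak BHB and dose.

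**Working it through.** **Step 1. What the plan names against what it analyses.**

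| Item | Named as a dose concern | Endpoint in Table 1 | Primary outcome in section 7 | Summarised by dose in section 7 |
|---|---|---|---|---|
| Gastrointestinal symptoms | Yes (sections 4, 5.3, 6) | No | No | No |
| Any adverse event | Monitored (section 6) | No | No | No |
| pH, glucose, systolic pressure | Safety measures | Yes | Yes | Yes |
| BHB | Target level (section 5.3) | No | Yes | Yes |

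**Step 2. Numbers available.** Section 5.3 gives two strata, with 5 participants at each of two doses. The total is 2 × (5 + 5) = 20, which matches the plan's figure. Each dose has 5 + 5 = 10 participants, and each stratum-by-dose cell has 5. The plan gives no power calculation to reproduce.

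**Step 3. What a table by dose could show.** With no events among n, the exact two-sided 95% upper limit is 1 − 0.025^(1/n).

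- 0 of 10: 1 − 0.025^(1/10) = 0.308, or 31%.
- 0 of 5: 1 − 0.025^(1/5) = 0.522, or 52%.
- 1 of 10: the Clopper-Pearson upper limit is 0.445, or 45%.

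**Step 4. Would anything be seen?** The documents give no event rate for these doses, so the true rate is an assumption. The chance of at least one event among 10 is 1 − (1 − p)^10:

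| Assumed true rate p | Chance of at least one event in 10 |
|---|---|
| 5% | 40% |
| 10% | 65% |
| 20% | 89% |
| 30% | 97% |

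**Step 5. Would a test help?** For a two-sided Fisher test of 10 against 10 at the 0.05 level, power is about 6% for 10% v 30%, 30% for 10% v 50%, and 67% for 10% v 70% (all assumed rates). With 0 of 10 at the lower dose, 4 of 10 at the higher dose gives p = 0.087, and 5 of 10 is needed to reach p = 0.033. A significance test has little to offer, so counts with intervals are the right output.

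**Step 6. Independence.** Section 5.3 allows a person to take part once in each arm if the arm without SGLT2i is hard to fill. A pooled dose group of 10 could then contain between 5 and 10 different people. If repeat participants respond identically, the upper limit for no events lies between the 31% and 52% of step 3.

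**The case against.** The strongest reply is that the documents do not expect a gastrointestinal problem at the study doses. They place the distress typically at 714 mg/kg, above both. Section 5.3 states that the BHB level predicted at 500 mg/kg has been reached in heart failure patients without notable side effects. Section 6 reports the proposed doses in 15 HFpEF patients with no significant related adverse events. The ceiling sentence is about going beyond 500 mg/kg, not about 250 against 500. The plan also provides a light meal and free access to water, and it does monitor adverse events.

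Much of this stands, and it rules out three stronger readings.

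- A reader might infer that gastrointestinal distress is the effect expected to separate the two doses. The documents do not say so. What section 5.3 predicts to differ is BHB, at about 1–2 against about 3 mmol/L, and BHB is a primary outcome.
- A reader might infer that the dose will be chosen blind to symptoms, or that vomiting and unfinished drinks will go unrecorded. The documents support only that no recording of intake is specified. Vomiting would fall under any adverse event, and nothing stops the investigators from weighing symptoms informally.
- A reader might infer that incomplete intake will bias the dose-response analysis. The documents give no frequency or extent of incomplete intake, so any size put on this is hypothetical. For choosing a dose to carry forward, the level achieved under the assigned dose, incomplete intake included, is arguably the quantity of interest.

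The reply does not remove the gap. An expectation of few events in HFrEF is worth documenting, and the experience cited for these doses in section 6 is in HFpEF. Low precision is a reason to report descriptively, not a reason to report nothing.

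**Conclusion.** The point holds as a gap in collection and reporting. The documents use gastrointestinal risk to bound the dose, seek a dose free of significant safety concerns, and then specify neither a tolerability measure nor any summary of adverse events by dose. It should be fixed before enrolment, because solicited symptom and intake data cannot be recovered after the visit.

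The omission does not translate into a calculable error in any planned estimate. What can be sized is the precision of the missing table. Zero events would exclude true rates above 31% at a dose and above 52% in one stratum at a dose, assuming independent participants. The true event rates at 250 and 500 mg/kg are not given and may well be low. Nothing here bears on which dose is right.

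**What to change.** **Collection.** At the scheduled post-drink draws, have the staff already present complete a short fixed gastrointestinal symptom checklist, and record the share of the drink taken and any vomiting. Section 5.3 does not count a missed 30- or 90-minute draw as a deviation, so the form should be required at least at 60, 120, 180 and 240 minutes.

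**Section 7.** Add a descriptive safety outcome: the number of participants with any gastrointestinal symptom, and with any adverse event, by dose and stratum, with exact 95% confidence intervals and no significance test. Flag anyone enrolled in both arms, and state the number of different people behind each pooled count.

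**Peak BHB against dose.** Keep this analysis on assigned dose and report incomplete intake alongside it. Do not add a re-analysis that drops those participants, since that would select on an event occurring after dosing that may itself depend on dose.

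**Cost.** One form and one table, with no extra visit or procedure. The small downside is that solicited symptoms will run higher than unsolicited ones and will be less comparable with other studies, which the report should say.

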Prior to the ketone drink, we will collect blood –twice - in the fasted status (>8 hours of fasting) and then after a light breakfast. We will collect blood 6 times after ketone drink. There will be at most 8 blood draws as below.

Blood draw number	Approximate time of blood draw	Blood draw for endpoint assessment	Blood draw for storage
1	Fasting, prior to ketone drink		х
2	After light meal, prior to ketone drink		x
3	30 minutes after ketone drink		х
4	60 minutes after ketone drink	Х	x

5	90 minutes after ketone drink		х
6	120 minutes after ketone drink	X	x
7	180 minutes after ketone drink	x	x
8	240 minutes after ketone drink	x	x

Timepoints delinated here are approximate. We aim to draw blood as close to the timeline outlined here, but +/- 15 minutes from the timepoint is considered acceptable without deviation. Likewise, lack of blood draws at times not used for endpoint assessment will not be considered a deviation.

We preferentially enroll unique patients in this study (i.e. 20 different patients). However, in the event of difficult enrollment in the "no SGLT2i arm", participants currently taking an SGLT2i may enroll and hold the SGLT2i for at least 4 days (with the permission of their treating physician). This amount of time is similar to what is advised prior to some procedures (i.e. surgery). Therefore, participants could enroll twice in this study (in each arm).

A total of ~100 mL of blood will be obtained at this visit.

Blood samples will be stored (either within the Duke Heart Center or the Duke Molecular Physiology Institute) at -80C for later analysis. We may perform routine blood testing (metabolic panels, blood counts), comprehensive metabolomic/proteomic profiling from this peripheral blood, as well as other biomarkers, in addition to other testing, pending sufficient funding.

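### The protocol commits to adverse event monitoring only during the study visit; one call at about 24 hours would be a cheap, optional improvement

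*Combined protocol and SAP*

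**What the plan says.** Section 6 (Risks and Safety Assessment) contains the only statement on how adverse events are collected: "We will monitor for any adverse events throughout the study visit". The next sentence reads "The compound half-life is short as indicated above". Earlier in the same section the protocol gives the kinetics: "The half-life of BHB from the compound is 0.8-3.1 hours" and "The TMax ranges from ~1-3 hours", with the peak placed at around 60 minutes for the doses to be used here.

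Section 5.3 sets the schedule: "We will measure venous pH, glucose, blood pressure, and BHB every 60 minutes for 4 hours". The eighth and last blood draw is at 240 minutes, and a departure of up to "15 minutes from the timepoint is considered acceptable without deviation", so it may fall anywhere from 225 to 255 minutes. The ester is given on a single study date (Section 4). The time at which the visit ends is not stated.

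Section 6 also names two risks that need not appear within four hours. One is ketoacidosis in participants on an SGLT2 inhibitor. The protocol does not expect the ester to amplify it but says: "However, this potential risk will be outlined to participants who enroll in this study". The other is from phlebotomy: "There is also a very small chance (less than 1%) of infection at the blood draw site".

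No section available for review describes a follow-up call, a later visit or a reporting window after the visit. Consent and contact pages were removed before review, so this is a statement about the protocol text only.

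**The concern.** Aim 1 (Section 2) covers both pharmacokinetics and safety, and Section 1 says the results will guide dosing in a later randomized trial. If adverse events are sought only while the participant is on site, a report of no adverse events means none during roughly the first four hours. Anyone planning the next trial could take it to mean none after the dose.

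The question is whether the visit spans the period of exposure. At the short end of the stated half-life range it largely does. At the long end, a participant given 500 mg/kg could go home with BHB still clearly above the 0.5 mmol/L that Section 3 uses to define ketosis. What is at stake is the completeness of a descriptive safety record; no estimate or test is involved.

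**Working it through.** The plan gives no figure on this point, so there is nothing to reproduce. The check asks how much BHB remains at the last scheduled draw, using the protocol's own values.

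**Inputs**
- Half-life h: 0.8 to 3.1 hours (Sections 4 and 6).
- Peak after 500 mg/kg: about 3 mmol/L (Section 5.3). After 250 mg/kg: about 1 to 2 mmol/L (Section 5.3).
- Time of peak: 1 hour, the value Section 6 gives for these doses.
- Last draw: 4 hours, allowed range 3.75 to 4.25 hours (Section 5.3).
- Marker of exposure: 0.5 mmol/L (Section 3). It marks ketosis, not harm.
- Assumption: first-order decline after the peak. Section 4 also mentions capacity-limited elimination, so this is an approximation.

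**Formulas**
- BHB at time t = peak × 0.5^((t − Tmax)/h)
- Time to reach 0.5 mmol/L = Tmax + h × log2(peak/0.5)

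**500 mg/kg, peak 3 mmol/L at 1 hour**
- At 4 hours, h = 0.8: 3 × 0.5^(3/0.8) = 0.22 mmol/L.
- At 4 hours, h = 3.1: 3 × 0.5^(3/3.1) = 1.53 mmol/L.
- Time to 0.5 mmol/L: 1 + 0.8 × log2(6) = 3.1 hours, and 1 + 3.1 × log2(6) = 9.0 hours.
- Half-life at which BHB is exactly 0.5 mmol/L at the last draw: (4 − 1)/log2(6) = 1.16 hours (1.06 for a draw at 225 minutes, 1.26 at 255). Below that value there is no gap by this marker.

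**250 mg/kg, peak at 1 hour**
- Peak 1: 0.07 to 0.51 mmol/L at 4 hours; 0.5 mmol/L is reached at 1.8 to 4.1 hours.
- Peak 2: 0.15 to 1.02 mmol/L at 4 hours; 0.5 mmol/L is reached at 2.6 to 7.2 hours.

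**Would 24 hours be long enough?** As a deliberately extreme case, take a peak of 5 mmol/L (the top of the range in Section 4, read as BHB), the latest stated Tmax of 3 hours, and h = 3.1. At 24 hours: 5 × 0.5^(21/3.1) = 0.046 mmol/L. A 24-hour window covers the exposure in every stated case.

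**What could the added data show?**
- Site infection: at under 1% per enrolment, 20 enrolments give fewer than 20 × 0.01 = 0.2 expected events, and the chance of any is under 1 − 0.99^20 = 18%.
- With zero events of a given kind, the one-sided 95% upper bound is 1 − 0.05^(1/n): 26% for the 10 enrolments at each dose and 14% for all 20. This treats enrolments as independent, although a participant may enrol twice. The data can only be descriptive.

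**The case against.** The strongest reply is that this is a preference, not a flaw. Aim 1 goes on to say how it will be met, by serial sampling of pH, glucose, systolic pressure and ketones after an acute dose, and Section 4 describes the safety intent in the same terms. Those measurements span the expected peak and run to four hours. Even the latest stated Tmax, 3 hours, precedes the last draw. The one adverse effect of the product that the protocol describes, gastrointestinal distress, is tied to 714 mg/kg, and Section 5.3 stops at 500 mg/kg. The largest base-case value at 4 hours, 1.5 mmol/L, lies inside the range the study deliberately targets with its starting dose. All of this stands, and it keeps the point small.

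A reader might infer three stronger things that the documents do not support.

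- **That the short half-life is the protocol's reason for stopping at the visit.** That sentence follows the monitoring sentence but is never offered as a justification for the window.
- **That later events would be disregarded.** The text commits to monitoring during the visit and is silent afterwards. Participants may volunteer events, and instructions may exist on pages not available here. What is missing from the text is systematic collection.
- **That ketosis lasting 11 to 13 hours is expected.** Pairing a 3 or 5 mmol/L peak with Tmax 3 hours and h = 3.1 gives 11.0 or 13.3 hours to reach 0.5 mmol/L. However, Section 4 says 3 to 5 mmol/L is reached within 60 minutes, and Section 6 puts the peak at about that time for these doses. The late-peak case is useful only for checking that 24 hours is enough.

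It is also fair to say that a telephone call cannot measure pH or BHB and is a poor way to find a site infection, which may not be apparent by 24 hours.

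**Conclusion.** The point holds as an optional improvement to safety ascertainment. Following the protocol as written leaves events that first appear after the visit without systematic collection, in a study with safety in its first aim.

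The size is modest. After 500 mg/kg, BHB at 4 hours is about 0.2 to 1.5 mmol/L across the stated half-lives, and it stays above 0.5 mmol/L at the last draw only if the half-life exceeds about 1.2 hours. This rests on first-order decline from about 3 mmol/L at 1 hour.

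It would be tempting to read the remaining exposure as a quantified safety gap. The documents do not allow that. They link no adverse event to the declining tail, give no rate or timing of late events, and expect low risk at these doses. The number of events missed cannot be estimated and may be zero. The four primary outcomes in Section 7 are all at 1 hour, and neither they nor the planned analyses are affected.

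**What to change.** In Section 6, define the adverse event collection period as running from the drink to about 24 hours, closed by one scripted telephone contact per enrolment made by existing staff. The script should ask about symptoms such as gastrointestinal distress and, in participants on an SGLT2 inhibitor, symptoms that suggest ketoacidosis. Report the events descriptively by dose and SGLT2 inhibitor stratum, without tests of attribution, and state the collection period with the results.

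The cost is a short amendment and about 20 brief calls, with no extra visit or blood draw. The downsides are that the information is self-reported, some unrelated minor events will be recorded with no control arm to set them against, no pH or BHB value is obtained, and few site infections would be caught by 24 hours.
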